13.2.1 Mandatory Medical Device Reporting

Manufacturers are required to report to the FDA via an electronic equivalent of Form 3500A when they learn that any of their devices may have caused or contributed to a death or serious injury or has malfunctioned and the malfunction would be likely to cause or contribute to a death or serious injury if it were to recur (key terms are defined in 21 CFR 803.3.). Manufacturers must also report to the FDA when they become aware that their device has malfunctioned and would be likely to cause or contribute to a death or serious injury if the malfunction were to recur. Should such an event occur during this study, the appropriate device manufacturer will file Form 3500A with FDA's Center for Devices and Radiological Health as required by law.

14 Statistical Analysis Considerations

Following is a summary of the Statistical Analysis Plan for this study. Please refer to the separate SAP for detailed information.

14.1 Analysis of Primary Effectiveness Endpoint

The primary endpoint is the mean change in PAL from baseline at the 12 week visit. The PAL is calculated as the ratio of total daily energy expenditure to sleep energy expenditure, as described in Section 9.4.1. The study will be considered successful if the mean change in PAL is assessed for both study arms. In addition, in the event of a successful study, the following hypothesis test will also be performed.

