14.1.1 Hypotheses

The hypotheses associated with the primary endpoint are defined as follows:

$$\begin{aligned} H_0: \mu_t - \mu_c &= 0 \\ H_1: \mu_t - \mu_c &\neq 0 \end{aligned}$$

where μ_t is the mean change in PAL for the test patients (patients assigned to the POC arm) and μ_c is the mean change in PAL for control patients. If the null hypothesis is rejected, i.e., the conclusion of inequality is achieved, and the observed difference between the mean sample changes in PAL, $\bar{x}_t - \bar{x}_c$, is greater than 0, then higher physical activity level by the test group, as compared to the control group, will be considered demonstrated. For accuracy, non-wear time data will be excluded from analysis.

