14.2 Sample Size

The following assumptions were used to determine the sample size for the primary endpoint of mean change in PAL from baseline at 12 weeks:

- Patients will be assigned to either the test or control treatment group
- The primary analysis is an inequality comparison of the test treatment to the control treatment
- The standard deviation for both test and control treatments is 0.22.
- A difference between treatment groups of ≥ 0.1 is considered clinically significant (i.e., the minimal desired detectable difference between treatment groups)
- The difference between the treatment groups is expected to be 0
- Greater than 80% power is considered sufficient
- Statistical test will be performed with a two-sided 5% significance level

To maintain at least 80% power to detect a difference between treatment groups of 0.1 with a common standard deviation of 0.22, 77 patients per treatment group would be required for a total of 154 patients. Adjusting for potential 20% attrition, 93 patients per treatment group will be required for a total of 186 patients. An additional four patients will be enrolled in order to provide more data for the success calculation, thereby bringing the total sample size to 190.

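### The only definition of study success in the protocol is met once PAL change has been measured in both arms, so a null or negative trial could be reported as successful

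*Protocol*

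**What the plan says.** Protocol 14.1 defines the primary endpoint as mean change in PAL at 12 weeks and then sets the success criterion: "The study will be considered successful if the mean change in PAL is assessed for both study arms". It gives no threshold, direction, p-value or minimum amount of data. The between-arm test comes next, as an addition: "In addition, in the event of a successful study, the following hypothesis test will also be performed".

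Protocol 14.1.1 holds a separate rule that depends on the result. If the null hypothesis of equal mean change is rejected and the observed difference is above zero, "then higher physical activity level by the test group, as compared to the control group, will be considered demonstrated". That rule is not linked to study success.

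Protocol 14.2 treats the inequality comparison as the primary analysis and sizes the trial on it ("To maintain at least 80% power to detect a difference between treatment groups of 0.1 with a common standard deviation of 0.22"). It then goes from 186 to 190 patients with this reason: "An additional four patients will be enrolled in order to provide more data for the success calculation". No such calculation is described in either document.

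Protocol Section 14 calls itself a summary and refers to the SAP for detail. SAP 6 and 6.1 present the between-arm comparison without any success criterion and without any precondition. They also leave out the directional conclusion of 14.1.1. SAP 6.2 reaches 190 by way of attrition and other factors.

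**The concern.** A success criterion should separate results that support the trial's hypothesis from results that do not. Protocol Section 1 hypothesises that adding a POC may make patients more active, and Protocol 15.4 justifies the study by its potential to show this. The criterion in 14.1 depends only on whether the endpoint was measured, so it carries no information on that question.

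What is at stake is how the trial is reported. The SAP neither repeats the sentence nor withdraws it, so it remains the only stated definition of success. A report could truthfully say that the study met its protocol-defined success criterion when the difference is null or favours control, and a reader would take that as evidence of benefit. The early closure makes a non-significant result more likely than planned, and so makes this more than a theoretical risk.

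**Working it through.** **Inputs**
- Clinically relevant difference 0.1, SD 0.22 in each arm, two-sided 5%, at least 80% power, 77 per arm, expected difference 0 (Protocol 14.2, repeated in SAP 6.2).
- Rule for declaring higher activity: reject the null and observed difference above 0 (Protocol 14.1.1).
- 109 of 190 patients enrolled at closure (SAP 2). An equal split between arms is my assumption.

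**Step 1. Reproduce the plan's figure.** Normal approximation: n = 2 × (1.960 + 0.842)² × 0.22² / 0.1² = 76 per arm after rounding up. The two-sample t-test version (noncentral t) gives 76.95, hence 77. Power at 77 per arm is 80.0% by t and 80.5% by z. The stated 77 therefore reproduces, and it is the size for the between-arm test.

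**Step 2. Compare the two rules at 77 per arm.** The standard error of the difference is 0.22 × √(2/77) = 0.0355. The noncentrality is the true difference divided by 0.0355, which is 2.82 at a difference of 0.1. With 152 degrees of freedom, the chance of rejecting with a positive difference is the upper tail of the noncentral t beyond the 97.5% point of the central t.

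| True difference (POC minus control) | 14.1 success criterion met, given PAL change in both arms | 14.1.1 rule met |
|---|---|---|
| −0.1 | 100% | about 0% |
| 0 | 100% | 2.5% |
| 0.05 | 100% | 28.8% |
| 0.1 | 100% | 80.0% |

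The 100% column follows directly from the definition. It shows that the criterion does not respond to the result; it is not an error rate for any claim of benefit.

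**Step 3. Does the condition on the test matter?** A between-arm test of PAL change cannot be run without PAL change in both arms, and that is all the success criterion asks for. The condition therefore removes no test that could otherwise be done. Type I error and power are unchanged.

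**Step 4. After early closure.** 109/2 = 54.5 per arm gives about 65% power at 0.1 with no loss. With 20% loss, 54.5 × 0.8 = 43.6 per arm gives about 55–56%. The 14.1 criterion would be met in either case.

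**Step 5. The four extra patients.** 190 is 95 per arm, and 95 × 0.8 = 76 after 20% loss, against 93 × 0.8 = 74.4 without them. Attrition, the reason in SAP 6.2, is enough to explain the addition without any success calculation.

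**The case against.** The strongest reply is that the rule that counts is already in place. Protocol 14.1.1 says what must be observed before higher activity is claimed, 14.2 makes that comparison primary and powers it, and the SAP runs it unconditionally. On this view the sentence in 14.1 is a poorly named completion condition in a post-approval study of cleared devices, where the expected difference is stated as 0. A sponsor may define completion separately from demonstrated benefit.

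Most of this stands, and it rules out several stronger readings that a reader might infer:
- *The trial has no decision rule for its own question.* It has one, in 14.1.1.
- *The conditional clause distorts the test.* It does not (Step 3).
- *The criterion can never fail.* It would fail if PAL change could not be obtained in one arm. What it cannot do is fail because of the result.
- *The success calculation is a missing analysis.* The phrase may refer only to assessing mean change in each arm. It is undefined, but four patients in 190 have little effect.

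The reply does not remove the label. No other definition of success exists in either document, the SAP does not withdraw this one, and the SAP omits the directional conclusion that keeps completion and benefit apart. It is also fair to say that writing a new success threshold after closure would be post hoc, and the fix below avoids that.

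**Conclusion.** The success sentence in Protocol 14.1 is wrong as written. It names as success a feasibility condition that is met at every true difference, while the rule that answers the trial's question has a 2.5% chance of being met under no difference and an 80.0% chance at 0.1. Those two figures assume 77 analysed patients per arm, SD 0.22 and a two-sided 5% t-test.

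The consequence is limited to interpretation and reporting. No estimate, test, error rate or sample size is affected, and a specific claim of higher activity remains controlled by 14.1.1. The documents support the conclusion that a null or negative trial could be described as having met its success criterion. They do not support the conclusion that a false claim of benefit has become more likely under the planned test.

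**What to change.** 1. In Protocol 14.1, delete the success sentence and the clause that makes the test conditional on it. If a completion criterion is wanted, keep the sentence but label it as feasibility or completion only.
2. State in Protocol 14.1 and SAP 6 that the primary effectiveness conclusion rests solely on the existing 14.1.1 rule, and carry its directional part into SAP 6.1.
3. In Protocol 14.2, replace the success rationale for the four extra patients with the attrition rationale already in SAP 6.2.
4. The study was terminated effective 30 April 2020 and the SAP is dated 18 August 2020. Make the change as a dated clarification that uses the protocol's own rule and adds no threshold. In the final report, do not call the trial successful on the strength of the 14.1 criterion.

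The cost is wording only, with no new data, patients or analyses. The sponsor gives up a statement of success that would have held whatever the result.

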14.1.1 Hypotheses

The hypotheses associated with the primary endpoint are defined as follows:

$$\begin{aligned} H_0: \mu_t - \mu_c &= 0 \\ H_1: \mu_t - \mu_c &\neq 0 \end{aligned}$$

where μ_t is the mean change in PAL for the test patients (patients assigned to the POC arm) and μ_c is the mean change in PAL for control patients. If the null hypothesis is rejected, i.e., the conclusion of inequality is achieved, and the observed difference between the mean sample changes in PAL, $\bar{x}_t - \bar{x}_c$, is greater than 0, then higher physical activity level by the test group, as compared to the control group, will be considered demonstrated. For accuracy, non-wear time data will be excluded from analysis.

14.2 Sample Size

The following assumptions were used to determine the sample size for the primary endpoint of mean change in PAL from baseline at 12 weeks:

- Patients will be assigned to either the test or control treatment group
- The primary analysis is an inequality comparison of the test treatment to the control treatment
- The standard deviation for both test and control treatments is 0.22.
- A difference between treatment groups of ≥ 0.1 is considered clinically significant (i.e., the minimal desired detectable difference between treatment groups)
- The difference between the treatment groups is expected to be 0
- Greater than 80% power is considered sufficient
- Statistical test will be performed with a two-sided 5% significance level

To maintain at least 80% power to detect a difference between treatment groups of 0.1 with a common standard deviation of 0.22, 77 patients per treatment group would be required for a total of 154 patients. Adjusting for potential 20% attrition, 93 patients per treatment group will be required for a total of 186 patients. An additional four patients will be enrolled in order to provide more data for the success calculation, thereby bringing the total sample size to 190.

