3.3.4 Randomization

Subjects will be randomized according to the pre-specified randomization schedule following the confirmation of enrollment eligibility. Subjects will be randomized to either the treatment or control arm in a 1:1 ratio. The randomization will be based on random, permuted blocks and stratified by center. Randomization will continue sequentially regardless of a subject not being treated according to their randomization assignment.

4 Study Objectives

This study is designed to evaluate the effect of using a POC combined with SOC long-term oxygen therapy versus SOC long-term oxygen therapy alone on the physical activity level of subjects with COPD requiring long-term oxygen therapy. This study will also assess the effect on oxygen usage, quality of life, hospitalizations, and death and the safety of the device.

5 Endpoints

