6.2 Sample Size

The following assumptions were made while determining the required sample size:

- Patients will be assigned to either the treatment or control arm
- The primary analysis is an inequality comparison of the treatment and control arms
- The standard deviation for both arms is 0.22
- A difference ≥ 0.1 is considered clinically significant (i.e., minimal desired detectable difference)
- The difference between the arms is expected to be 0
- Statistical testing will use a two-sided 5% significance level with at least 80% power

At least 154 subjects (77 per treatment arm) are required to analyze the primary effectiveness endpoint with statistical power. To account for up to 20% attrition and other factors, up to 190 subjects (95 per treatment arm) are required to ensure adequate power is maintained for the primary effectiveness endpoint.

7 Analysis of Secondary Endpoints

The secondary endpoints are evaluated at the week 12 follow-up visit and compare the treatment and control arms. Analysis of the secondary endpoints evaluates the following:

- 1. Change in average daily oxygen usage from baseline
- 2. Change in Quality of Life from baseline
 - a. St. George's Respiratory Questionnaire
 - b. Hospital Anxiety and Depression Scale
- 3. Change in Six Minute Walk Test (6MWT) distance from baseline
- 4. Frequency of COPD exacerbation
- 5. COPD or other respiratory condition-related inpatient hospitalization ≥ 24 hours
- 6. Change in average number of steps taken/day (non-hospital days) from baseline
- 7. Mortality due to COPD or other respiratory condition (primary cause of death)
- 8. All-cause mortality

For secondary endpoints 1 and 6, the baseline and week 12 follow-up visit values are the average value during the first and twelfth weeks of the study, respectively. For accuracy, only wake- and wear-filtered ActiGraph data will be used in the analysis.

The assessments used in secondary endpoints 2 and 3 are performed at both the baseline and week 12 follow-up visits.

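### The 20% attrition allowance is too small: 77 analysable per arm needs 97 enrolled per arm (194), so neither the protocol's 186 nor the SAP's 190 keeps the stated 154 at 20% loss

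*Protocol*

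**What the plan says.** Protocol 14.2 gives the planning inputs. On variability it says: "The standard deviation for both test and control treatments is 0.22". On the effect to be detected it says: "A difference between treatment groups of ≥ 0.1 is considered clinically significant". On the test it says: "Statistical test will be performed with a two-sided 5% significance level". The power target is at least 80%, and the number needed to reach it with these inputs is given as follows: "77 patients per treatment group would be required for a total of 154 patients". The attrition step comes next: "Adjusting for potential 20% attrition, 93 patients per treatment group will be required for a total of 186 patients". Four more patients are then added, bringing the total to 190. The reason given for them is extra data for the success calculation; attrition is not mentioned.

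SAP 6.2 keeps the same inputs and the same minimum of 154 (77 per arm), and goes straight to the final total: "To account for up to 20% attrition and other factors, up to 190 subjects (95 per treatment arm) are required to ensure adequate power". It does not show the intermediate 93 or 186.

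SAP section 6 limits the primary analysis to subjects who have PAL values at both baseline and week 12. Imputation of missing week 12 PAL appears only as a sensitivity analysis (SAP 11.5). Each patient lost before week 12 therefore reduces the number analysed.

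**The concern.** An attrition allowance should give an enrolment that still contains the required number after the stated share of enrolled patients has been lost. The required number must then be divided by one minus the loss rate. The protocol's 93 is lower than that division gives, and matches what results if 20% is added to 77 instead.

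At stake is whether two statements are true: the protocol's that 186 allows for 20% attrition, and the SAP's that 190 maintains adequate power with up to 20% attrition and something to spare. Because the primary analysis uses only complete pairs, it has no other protection against loss.

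**Working it through.** **Inputs.** Difference 0.1, SD 0.22 in both arms, two-sided 5%, power at least 80%, attrition 20% (Protocol 14.2 and SAP 6.2); 1:1 allocation (SAP 3.3.4: "Subjects will be randomized to either the treatment or control arm in a 1:1 ratio"); t-test for continuous variables (SAP 11.6).

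**Step 1: reproduce 77.**
- Normal approximation: n = 2 × [0.22 × (1.960 + 0.842) / 0.1]² = 75.98, so 76 per arm.
- Two-sample t-test, with power from the noncentral t on 2n − 2 degrees of freedom and noncentrality 0.1 / (0.22 × √(2/n)): 79.5% at n = 76 and 80.03% at n = 77. The smallest adequate n is 77.

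The stated 77 reproduces exactly with the t-test.

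**Step 2: reproduce 93.**
- 77 × 1.2 = 92.4, rounded up to 93 per arm, 186 in total. This matches.
- 77 / 0.8 = 96.25, rounded up to 97 per arm, 194 in total. This does not match.
- Starting from 76 does not give 93 either: 76 × 1.2 = 91.2, rounded up to 92, and 76 / 0.8 = 95.

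**Step 3: what each size leaves at 20% loss.**

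| Enrolled per arm (total) | Left per arm (total) | Power, noncentral t |
|---|---|---|
| 93 (186) | 74.4 (148.8) | 78.6% |
| 95 (190) | 76.0 (152) | 79.5% |
| 97 (194) | 77.6 (155.2) | just above 80% |

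The reference value is 80.0% at 77 per arm. By the normal approximation, 76 per arm gives 80.0% and 74.4 gives 79.2%.

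**Step 4: attrition that each total tolerates while keeping 154.**
- 186: 1 − 154/186 = 17.2%.
- 190: 1 − 154/190 = 18.9%.

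**Step 5: the trial as it ended.** SAP section 2 reports 109 of 190 enrolled at closure. With an even split (54.5 per arm), no attrition and the same difference and SD, noncentral-t power is 65.2%.

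**The case against.** The best defence is that the operative number is 190, not 186. Against 194, 190 is short by 4 patients in total (2 per arm). At 20% loss it leaves 76 per arm, one below the target, and by the normal approximation 76 is enough for 80%. Neither document prints a sample-size formula.

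Much of this stands on size. It does not make the sentences correct. Both documents state 77, which is the t-test answer, and the SAP names the t-test. Switching to the approximation would contradict the stated 77, and would still not rescue 93, which leaves 74.4. The four extra patients reduce the gap, but the protocol gives another reason for them, and crediting all four to attrition still leaves 152 against 154.

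A second defence is that the study closed early and SAP version 1.0 (18 Aug 2020) was written afterwards, so nothing about enrolment can change. That is right, and it limits the point to a correction of the record.

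A reader might also infer things that the documents do not support:
- That the plan was 8 patients short. That compares 194 with the intermediate 186, which was never the planned enrolment.
- That the SAP repeats the whole calculation. It carries 154, 190 and the 20% claim, but neither 93 nor 186.
- That the plan states the multiplication by 1.2. The match is exact, but the mechanism is inferred. The error does not depend on it, because 93 × 0.8 = 74.4 whatever the route.
- That this error left the trial underpowered. Stopping at 109 did far more.

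**Conclusion.** The point holds, and it is small. Read as a share of enrolled patients, 20% attrition requires 97 per arm (194). Neither 186 nor 190 keeps the 154 that both documents require, and SAP 6.2 contradicts itself by 2 patients, with nothing left for other factors. The cost in planned power is about half a percentage point at 190 (79.5% against 80.0%) and about one and a half at 186 (78.6%). These figures rest on the documents' own difference, SD and two-sided 5% level, on equal loss in both arms, and on the t-test. The error had no material bearing on the power achieved, since enrolment ended at 109.

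**What to change.** No added enrolment and no change to the analysis. Leave the 20% figure in place as the planning assumption actually made, and leave the mention of other factors, since it may be the SAP's only trace of the four patients added for another reason. Substituting 18.9% for 20% would present a back-calculated rate as if it had been planned.

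Add a short statement to SAP 6.2, and wherever the design basis is reported, to this effect: *Retaining 77 analysable subjects per arm after 20% attrition would have required 97 per arm (194). The planned 190 would have left 152 analysable at 20% attrition, with 79.5% power (two-sample t-test, difference 0.1, SD 0.22), and tolerates at most 18.9% attrition for 80% power. Enrolment stopped at 109.*

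The cost is a few sentences and a slightly less favourable description of the design.

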14.3 Analysis of Secondary and Exploratory Endpoints

The full list of all secondary and exploratory endpoints can be found in Section 5.3. The mean changes from baseline in continuous secondary and other endpoints will be compared between treatment groups via independent samples t-tests, or a non-parametric equivalent as appropriate. General Linear Modeling will be used to assess the impact of potentially influential covariates.

For comparisons of categorical variables, a chi-square test (if appropriate) or Fisher's exact test will be used. Standard logistic regression will also be fit to these endpoints to include center effects and relevant covariates.

For certain variables associated with only one treatment arm, such as POC usage, summaries and estimation, including 95% confidence intervals, may be provided, with no formal hypothesis test performed.

The frequencies of each individual type of adverse event will be summarized along with a 95% exact binomial upper confidence bound. Adverse events, including UADEs, will also be summarized based upon seriousness, severity and relation to the procedure and the device. Individual adverse events will be listed for both groups, including time to event and resolution.

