The purpose of this Statistical Analysis Plan (SAP) is to summarize the statistical methodologies being used to determine the required sample size for and to analyze all endpoints associated with the use of portable oxygen concentrators (POC) combined with standard of care (SOC) long-term oxygen therapy (LTOT) (treatment) versus SOC alone (control) for 12 weeks among subjects prescribed long term oxygen therapy for diagnosed COPD.

2 Early Study Closure

Due to the outbreak of 2019 Novel Coronavirus (COVID-19) in the United States in March 2020, in particular because of the inherent health risks in this for COPD patients on LTOT and the likely negative impact to their Physical Activity Levels (PAL) (i.e., the patient population and primary endpoint for this study, respectively), the decision was made to prematurely terminate the study effective April 30, 2020. At the time of study closure, 109 of the planned 190 subjects (57%) had been enrolled, of which only 3 were still actively participating in the study.

The following impacts of the COVID-19 outbreak from March 2020 through the final study site closure will be summarized in the final report, where applicable:

- A listing of all subjects impacted by COVID-19-related study disruption, including how they were impacted, along with any related analyses and/or discussions as appropriate
- Analyses and corresponding discussions that address the impacts of the implemented contingency measures (e.g., trial participant discontinuation from investigational product and/or study, alternative procedures used to collect critical safety and/or efficacy data) on the safety and efficacy results for the study
- A summary of the reasons for failing to collect any efficacy endpoints, including identifying specific limitation imposed by COVID-19 leading to the inability to perform the protocol-specified assessment

3 Study Design

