For exploratory endpoint 5, the baseline and week 12 follow-up visit values are the average value during the first and twelfth weeks of the study, respectively. For accuracy, only wear-filtered ActiGraph data will be used in the analysis.

Exploratory endpoints 2-5 will only be summarized with descriptive statistics and will not have formal hypothesis testing performed.

9 Analysis of Adverse Events

All adverse events occurring during the study will be summarized by type, seriousness, Investigator-reported relatedness (to the study procedure and the LTOT, POC, and ActiGraph devices), severity, and outcome with the number of events experienced and the number and percentage of subjects experiencing the event. Adverse events will also be summarized in a listing. No formal hypothesis testing will be performed.

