11.6 Data Summaries

Unless otherwise stated, data will be summarized as followed:

- Continuous variables will be summarized with the count, mean, standard deviation, median, and range. Hypothesis testing will use the t-test (or Wilcoxon rank-sum test).
- Categorical variables will be summarized with counts and percentages. Hypothesis testing will
 use the chi-squared test (or Fisher exact test).
- Level of significance (α) for statistical testing will be 0.05 and two-sided.

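### The SAP drops the exact upper confidence bound and the UADE summary that the protocol promises for adverse events, so it does not show the uncertainty around zero or low counts

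*Protocol*

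**What the plan says.** **Protocol 14.3.** The bound applies to every event type: the frequency of each one "will be summarized along with a 95% exact binomial upper confidence bound". The next sentence reads: "Adverse events, including UADEs, will also be summarized based upon seriousness, severity and relation to the procedure and the device". Individual events are then to be listed for both groups, with time to event and to resolution.

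**Protocol 14.4.** The safety evaluation uses the intent-to-treat set, defined there as all randomised patients.

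**SAP Section 9.** Events are broken down by type, seriousness, relatedness (to the procedure and to the LTOT, POC and ActiGraph devices), severity and outcome, "with the number of events experienced and the number and percentage of subjects experiencing the event". It ends: "Adverse events will also be summarized in a listing. No formal hypothesis testing will be performed". It mentions no confidence bound, UADE category or arm.

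**SAP 11.6.** The general default adds no interval: "Categorical variables will be summarized with counts and percentages".

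**SAP 5.4 and 11.1.1.** Adverse events are listed under Endpoints. The ITT set is the primary set for all endpoints, but it admits only randomised patients who began oxygen therapy, received an ActiGraph and have at least baseline ActiGraph data.

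**SAP Sections 2 and 12.** The study was stopped effective 30 April 2020, when "109 of the planned 190 subjects (57%) had been enrolled". The SAP is version 1.0, dated 18 August 2020.

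**The concern.** A safety statistic written into the protocol is missing from the analysis plan, and that plan was finalised after an open-label trial had closed. No reason is recorded. SAP Section 4 names the safety of the device as something the study assesses.

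The omission matters more because of the early stop. The upper bound on a risk after zero events is roughly inversely proportional to the number of patients observed, so stopping at 57% of plan widens it by about 190/109 = 1.74 times. A table of counts and percentages shows the same 0% whether 54, 95 or 190 patients were observed. The bound is the one planned statistic that would show the difference.

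The denominator is a second problem. If the SAP's ITT set governs the safety tables, a randomised patient with no baseline activity data leaves them, although the protocol would count that patient.

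**Working it through.** **Stated figure.** 109/190 = 57.4%, which reproduces the SAP's 57%. Neither document gives an adverse event rate or a value for the bound, so there is nothing else to reproduce.

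**Inputs.** 190 planned, 95 per arm (SAP 3.1); 109 enrolled (SAP 2); 1:1 allocation (SAP 3.3.4). The actual split is not given, so 54 or 55 per arm is an assumption. The protocol does not say whether the bound is one-sided, so both readings are shown.

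**Formula.** The exact (Clopper-Pearson) upper limit U for x events in n patients:

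- x = 0, one-sided 95%: U = 1 − 0.05^(1/n)
- x = 0, upper end of a two-sided 95% interval: U = 1 − 0.025^(1/n)
- x = 1: the 0.95 (or 0.975) quantile of Beta(2, n − 1)

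Examples: 1 − 0.05^(1/109) = 0.0271; 1 − 0.05^(1/54) = 0.0540.

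| Patients | 0 events, one-sided | 0 events, two-sided | 1 event, one-sided | 1 event, two-sided |
|---|---|---|---|---|
| 190 (planned, pooled) | 1.6% | 1.9% | 2.5% | 2.9% |
| 109 (enrolled, pooled) | 2.7% | 3.3% | 4.3% | 5.0% |
| 95 (planned, one arm) | 3.1% | 3.8% | 4.9% | 5.7% |
| 55 (about half of 109) | 5.3% | 6.5% | 8.3% | 9.7% |
| 54 (about half of 109) | 5.4% | 6.6% | 8.5% | 9.9% |
| 45 (illustration: smaller denominator) | 6.4% | 7.9% | 10.1% | 11.8% |

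The last row shows what happens if the arm's denominator shrinks, whether through attrition or through the SAP's ITT definition. The documents do not say how many patients that would remove.

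**Chance of seeing no event at all.** For an assumed true risk of 2%, chosen only for illustration, the probability is (1 − 0.02)^n: 0.02 at 190, 0.11 at 109, 0.15 at 95 and 0.34 at 54.

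**Which denominator applies.** Protocol 13.1.3 lists fires, burns, electrical shock and low oxygen from malfunction as LTOT-related. Both arms receive LTOT (SAP 3.2.1), so for those events the pooled figure is relevant as well as the by-arm one. For events specific to the POC, only the POC arm is informative.

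**UADEs.** In the text supplied, the term appears only in Protocol 14.3. Protocol 13.1 does not define it, and Protocol 13.2.2 describes classification by seriousness, relatedness and severity. No written rule says which events fill the promised summary.

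**The case against.** The strongest reply is that this is only a reporting mismatch. Adverse events carry no hypothesis test or decision rule. Protocol Section 14 calls itself a summary and refers to the SAP for detail. The SAP is more specific than the protocol on relatedness and adds outcome. A reader can compute the bound from the published counts. SAP Section 2 states the enrolment shortfall and promises discussion of how COVID-19 contingency measures affected the safety results.

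Much of this stands, and it limits the weight of the point. Two parts do not. A summary of a plan should not promise a statistic that the plan lacks. A reader can rebuild the bound only if the arm and the denominator are clear, and on the denominator the two documents disagree.

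Stronger readings are tempting but not supported:

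- A reader might infer that a zero count will be taken as absence of risk. Neither document says so; the SAP simply leaves the uncertainty unshown.
- A reader might infer that the SAP names no denominator. It does so indirectly, through SAP 5.4 and 11.1.1. The trouble is that this set differs from the protocol's.
- A reader might infer that UADEs have no source data. The event form is not among the documents, and event type, the existing classifications and the 13.1.3 list could support a retrospective rule. What is missing is the rule.
- A reader might infer that the listed hazards are rare and confined to the POC arm. The documents give no rates, and the list is LTOT-related.
- A reader might treat 3.1% as a planned safety precision. The sample size was set on PAL alone; 3.1% is only what 95 patients would have given.

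**Conclusion.** The point holds as a discrepancy between protocol and SAP. The exact upper bound and the UADE summary are promised in one document and absent without explanation from the other, which is dated after closure. Presentation by arm is not stated, and the safety denominator conflicts.

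At zero events the one-sided bound is 2.7% for all 109 patients (two-sided upper limit 3.3%) and about 5.4% for a POC arm of 54 (two-sided 6.6%). At the planned sizes the one-sided figures are 1.6% and 3.1%. These rest on an even split and on every patient being followed for the full 12 weeks. Attrition or a narrower analysis set would raise them.

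The weight is minor to moderate: a cheap improvement to what can be said about uncommon harms. No conclusion on the primary endpoint changes.

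**What to change.** In SAP Section 9:

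1. For each adverse event type, report by arm and pooled the number of patients with the event over all randomised patients, the percentage, and the exact binomial 95% upper bound. State whether the bound is one-sided or the upper end of a two-sided interval.
2. State the zero-event bound at the achieved size, pooled and for each arm. This is needed because the protocol wording does not clearly require a row for event types that never occurred.
3. State that the safety tables use all randomised patients, as in Protocol 14.4, and not the SAP's ActiGraph-dependent ITT set.
4. Settle the UADE commitment. Either define UADEs against the anticipated events in Protocol 13.1.3, name who applies the rule, and report them; or record why the line was dropped. The LTOT list there is open-ended, so the rule must say how unlisted events are handled.

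The cost is a paragraph of text and one more table column, with no new patients or visits. If UADEs are kept, add a retrospective review of recorded events, made after closure in an unblinded trial, which should be disclosed. The downside is that the safety figures will look less favourable.
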